8.2.1 Clinical Evaluations

Physical examination

Participants will be examined at screening visit by board certified neurologist and movement disorder specialist with focused examination:

general, cardiopulmonary auscultation, neurologic exam with focus on motor or other system disorders (such as sensory, musculoskeletal) related to Parkinson's. There will also be UPDRS and request for video recording. Video record would require separate signed informed consent as per NIH protocol. Video recording is done for research purpose only (quality assessment by averaging scores of in-person rater with a separately blinded video rater).

Examination with requested video recording as per above will be repeated on day of discharge (post-intervention). Examination as per above will also be repeated on day of admission (pre-intervention), without request for video recording unless a significant clinical finding is observed in difference from the screening visit.

Vital signs and Heart rate variability

Vital signs will be done as per routine care in the Metabolic Unit and will also include daily orthostatic check to be done by Metabolic Unit staff or credentialed study investigator. Daily heart rate variability will be performed with pre/post intervention (daily days 1-7 and at week 3) heart rate responses to a) deep breathing at 6 cycles per minute (5 cycles E:I ratio) and difference between average max and min heart rates; and b) Valsalva Ratio (HR max : HR baseline) with Valsalva Maneuver x 15s at 30-40 mmHg (days 1, 7, and week 3).

Radiographic or other imaging assessments

ECG – ECG will be performed at screening or Day 1 of admission (depending on availability), however must be performed prior to diet intervention. A routine ECG will be performed for confirmation of normal cardiopulmonary function. If arrhythmia is detected, Cardiology will be consulted and incorporating their recommendations, decision about remaining or withdrawing from the study based upon the underlying etiology sinus (more likely stay in the study) vs. non-sinus rhythm aberrancy (more likely withdraw from study) as per inclusion/exclusion criteria.

EEG - regional changes in spectral power (theta, alpha, beta) and nonlinear corticocortical synchronization measure via phase lag index (focusing on frontotemporal, parietotemporaloccipital areas

Abbreviated Title: Tolerability and efficacy of ketogenic diet in Parkinson's Disease

Version Date: 04/19/2021

in alpha1 and alpha2 frequencies, and reduction in theta power in temporal-central regions) as per Chaturvedi et al, 2019.

EEG will be performed pre and post intervention in 7SW Neuro Testing area for a period of 20-30 minutes (1 hour session), under the supervision of a neurophysiologist and/or a neurologist trained in the technique (AI).

8.2.2 Biological specimen collection and laboratory evaluations.

Blood tests will be drawn twice daily for plasma beta-OHB levels and plasma dopamine through contracted vendor(s), to be determined based on competitive bid process and stored at -4 C as per recommended processing/batching. Blood draws will also occur on screening visit, hospital days 1 and 7 of admission, and week 3 visit for metabolic tests at a CLIA certified laboratory (NIH Clinical Center Laboratory) as per section 8.2.2 below.

Blood draws: 1 x (screening) + twice daily (admission days 1-6) + 1x (admission day 7) + 1x (week 3 final visit)

Study total: - volume of blood: 38 small tubes (1-2 mL each), approximately 40-80 mL
- blood draws: 15

8.2.3 Correlative Studies for Research/Pharmacokinetic Studies

Special assays or procedures required:

Continuous glucose monitoring (Freestyle Libre Pro System sensor, Abbott)

The monitor will be provided to participants upon enrolling at the screening visit (#1) to obtain one week of baseline data on usual diet, and continued for the duration of the admission. Two weeks of data are provided in the system memory. If there is a delay between the screening visit and the admission, participants will be instructed to stop the monitor at one week in order to preserve the second week memory storage for the admission.

Venous beta-OHB level and dopamine level

Blood draws will be performed at defined intervals twice daily - at 7am, and at 2 hours after dinner (8pm).

Timing of the blood draws is regarded as important to be as accurate as possible. Plasma dopamine will be tested on inpatient days 1-3, and plasma BOHB will be tested on inpatient days 1-7 and at week 3. The testing and reporting will be done in accordance with CLIA-certified NIH Clinical Center Core Laboratory.

Respiratory exchange ratio (quotient), pCO2:pO2

Will be performed on the Metabolic Cart at screening and week 3 outpatient clinic visits as per previously described method (Hall 2015, 26278052)

Metabolic labs (blood): Hgb A1c, lipid panel, insulin, glucose, cortisol, TSH, T3, free T4,, BDNF

Will be drawn day 1, day 7, and week 3 (final study visit), except for HgbA1C (screening, week 3) and lipid panel (screening, day 7, week 3)

Non-heparinized sterile tube will be used for transport / storage in the NIH Clinical Center Core Laboratory. The testing and reporting will be done in accordance with CLIA-certified NIH Clinical Center Core Laboratory.

Electrolytes (BMP, Magnesium) will be checked daily on inpatient days 2-6. If there is abnormality possibly or probably attributed to the intervention or determined to be medically significant by study

Abbreviated Title: Tolerability and efficacy of ketogenic diet in Parkinson's Disease

Version Date: 04/19/2021

investigators, it will be repeated on study days 6 and 7 and appropriate additional steps taken (e.g. hydration, anti-nausea medication, decreasing the lipid or MCT ratio of the diet, and possibly additionally including blood gas monitoring / transfer to ICU) in coordination with metabolic unit staff and the independent medical monitor.

Daily survey: Parkinson symptoms, ketoinduction symptoms and gastrointestinal motility

Two surveys will be administered daily, one detailing common Parkinson-related motor and non-motor symptoms (drawn from PI / AI clinical experience) as well as typical keto-induction symptoms (adapted from Harvey et al, 2018) and the other survey detailing gastrointestinal motility, adapted from IFFGD, URL: <https://www.iffgd.org/publications-library/library/341.html>

Blood and urine samples will be discarded as per routine policy.

8.2.4 Samples for Genetic/Genomic Analysis

PD inherited genes and family/linkage studies will be reviewed when available (prior enrollment in 01-N-0206 or other neurogenetic study). There will be no samples collected for genetic analysis under this protocol.

8.2.4.1 Description of how privacy and confidentiality of medical information/biological specimens will be maximized

Participants will be provided a study number, and storage/reporting will be only via this number. Study number will be linked to PHI only via a document maintained by unblinded NIH staff investigator not involved with study measurements (biostatistician) that will be removed from other investigators except for instances of unblinding due to adverse events or study withdrawal.

Measures of securing participants' PHI will be maintained as follows:

- Generation of study number by unblinded investigator (AI) in place of PHI for records of independent / dependent measures
- No PHI in daily measurement records (study number and recorded values, including daily self-report worksheets)
- All records maintained in locked cabinet or on NIH Secure server
- PHI for purpose of clinical care provided during admission maintained on password protected CRIS electronic medical record
- Data sharing with other researchers such as NINDS supervisors, co-workers, or Grand Rounds will be in de-identified fashion, except where Video Consent was obtained with provision of removing facial / identifying features was provided to participant but declined
- Data will not leave NIH except in the format of publication or presentation at professional meeting as per Data Sharing bullet item above

8.2.4.2 Management of Results

Results will be provided to participants in two formats: a discharge summary and a debriefing on the day of discharge or as otherwise determined with the participant. The discharge (DC) summary will include all laboratory results, including lipid profile, A1c, insulin, that in combination with blood pressure/height/weight/BMI and body fat % (bioelectric impedance) are significant to the metabolic and cardiovascular health, e.g. criteria for metabolic syndrome, HOMA-IR (insulin resistance calculation), and Framingham Risk score. DC summary will also include results of clinical assessments (e.g. Parkinson motor and non-motor symptoms / phenotypes / severity) and validated rating scales such as UPDRS, MOCA, and NMSS. Results

Abbreviated Title: Tolerability and efficacy of ketogenic diet in Parkinson's Disease

Version Date: 04/19/2021

will not include ketosis values, EEG results, and cognitive / physiology / autonomic measures obtained for research purposes that lack current health implication. The debriefing will review DC summary results as well as give opportunity for researcher (PI / Metabolic Unit staff) to present clinical synopsis and share aspects of the participant's research data as per expressed interest, as well as to provide education on diet given, general dietary recommendations, and summary of the intervention and research overview. Participants will be invited to review any publications and will be contacted for permission prior to presentation of any video.

The NIH Clinical Center Laboratory is CLIA certified, CLIA ID Number - 21D0665373

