that certain medications, medication dosages, or DBS status will interact with dietary composition, either ketogenic or standard at standard protein intake. Study raters will remain blinded to diet group, because randomization scheme will be kept only by biostatistician and intervention status will be known otherwise only by nutrition staff, none of whom are involved in study rating. A possible exception is unblinding due to serious adverse event determined by study PI (non-rater) in consultation with safety monitor in which participant continues in the study, in which case data will be demarcated and not included in statistical analysis. Prior to admission, participants will be instructed to complete a log for 1 week of activities and diet at home. Upon admission to the Metabolic Unit and during hospital day 1, they will continue a regular, healthy hospital diet (carbohydrate predominant) and undergo baseline testing in mobility, physiologic and cognitive measures as per Section 3, Objectives and Endpoints). On hospital days 2-7, they will begin one of two diets: diet A, MCT-KD, according to set macronutrient ratios by daily energy: lipid 80% (25% of which is MCT oil), carb 5-10%, protein 10-15%, expected to be better tolerated than traditional NK, vs. diet B, standard American diet, lipid 30-35%, carb 55%, protein 10-15%. The goal is study time series of betaOHB, respiratory quotient, and continuous glucose ketosis measurements with tests of symptomatic impairment, with the hypothesis that nutritional ketosis augments mitochondrial function within hours of keto-induction and provides further benefit over days due to better functional neurotransmitter supply to key motor and cognitive synapses, aside from any long-term disease modification. Added benefits of an inpatient trial include monitored adherence and a look at biomarkers such as respiratory quotient in the metabolic chamber (CO₂:O₂ expected to go down due to diet), as well as easier access to daily repeated testing such as cognitive focused testing on executive function, memory and learning, as well as quantitative motor assessment of bradykinesia (keyboard, 9-hole pegboard), blinded UPDRS, and pain / fatigue assessment by subjective report.

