6.3 MEASURES TO MINIMIZE BIAS: RANDOMIZATION AND BLINDING

As described in Section 9.2 (refer for details), study participants will be randomized after screening visit by study biostatistician. The intervention allocation will be withheld from all study investigators and raters until after the conclusion of all measurements, who will remain blinded to participant allocation for the duration of the study. Refer to Section 9 for details of randomization.

The study nutrition staff will remain unblinded in establishing participant-individualized meal plans. S/he will not disclose any diet details of the admitted participants and will not participate in any of the study measurements. Other investigators will be blinded except due to adverse event or inadvertent event.

Nutrition staff (CC Nutrition Department) will design the blinded diets according to the macronutrient ratios and MCT oil supplementation specified in the study (from calculated daily total energy expenditure by gas exchange on screening visit using Wier formula). Aside from the addition of MCT oil comprising 25% of daily lipids, the diet will be similar to what was used in existing study at the NIH CC Metabolic Unit, NCT03255031 Ketogenic Diet in Alcoholism, as per clinicaltrials.gov description:

Dietary Supplement: Ketogenic Diet (KD) / Standard American (SA) Snacks and Shakes

Abbreviated Title: Tolerability and efficacy of ketogenic diet in Parkinson's Disease

Version Date: 04/19/2021

“Ketogenic Diet (KD) / Standard American (SA) Meals and Shakes: Participants will be randomized to a meal plan of either a ketogenic diet (KD) or standard American (SA) diet at the time they sign the consent. For each meal at breakfast, lunch and dinner, the diets will consist of SA meal (carbohydrate rich) or KD meal depending on treatment randomization... []...To ensure that the diet is double blind...[]...solid snacks are always ketogenic and shakes are either KD or SA.”

From conversation with NIAAA study PI and study nutrition staff, when participants were asked about which diet they believed they received, they usually thought they were receiving ketogenic diet, which appears to support the integrity of the dietary blind.

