1 STATISTICAL CONSIDERATIONS

9.1 STATISTICAL HYPOTHESIS

Primary hypothesis:

Nutritional ketosis supplemented by MCT oil is feasible within a Parkinson Disease cohort as defined by an acceptable retention rate and outpatient adherence.

Primary outcome: Feasibility of nutritional ketosis(ketogenic diet with 80% lipid including MCT oil, 10-15% protein, 5-10% carbohydrate), in Parkinson Disease cohort defined as a composite outcome meeting all of the following criteria: recruitment target of 32 or as per interim power analysis defined in Section 9.4.6; retention rate > 80% at study end; adherence to ketogenic diet in the outpatient portion defined as mean carbohydrate energy intake <10%, and intervention is acceptable to all participants by Likert scale \geq 2/4 of likelihood of using this therapy in the future and effectiveness in symptom reduction, from all study participants at 3 weeks.

Secondary hypothesis:

Abbreviated Title: Tolerability and efficacy of ketogenic diet in Parkinson's Disease

Version Date: 04/19/2021

Nutritional induced ketosis (NK) increases mobility based on TUG score in a Parkinson Disease cohort at 7 days compared to usual diet (35% lipid, 10-15% protein, 50-55% carbohydrate). Secondary outcome: timed Up & Go test (TUG score) at study day 7 (fastest of three trials)

$H_0: \mu_1 = \mu_2$, where μ_1 and μ_2 are the population means for the NK diet group and usual diet group respectively vs. $H_1: \mu_1 \neq \mu_2$.

Exploratory hypotheses:

Hypothesis A: Nutritional ketosis improves PD symptomatology in cognition (improved attention, recall, and executive function, and motor function akinesia and tremor within six days, as assessed by: Stroop word-color interference latency (executive function), n-back recall task (attention and working memory), simple reaction time (akinesia); fingertap speed and rhythm MN and PQ keyboard tasks (fine motor), and autonomic function (heart rate variability at rest and with deep breathing / Valsalva Maneuver tests)

Hypothesis B: The mechanism of symptomatic reduction of NK in PD is both augmented mitochondrial metabolism (direct, rapid) and augmented neurotransmitter and growth factor synthesis (indirect, delayed), especially GABA and dopamine, as assessed by resting state EEG spectral power, phase coherence, and M1 waveform normalization. Accordingly, effect sizes for exploratory outcomes will be greater at 3 weeks than 7 days.

Exploratory outcomes daily (days 1-7), week 3

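### The default discharge-day debriefing can expose a blinded investigator, and through participants the week-3 rater, to the inpatient allocation before the week-3 measurements

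*Combined protocol and SAP*

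**What the plan says.** Three parts of the protocol bear on who may know the inpatient diet, and when.

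- **Section 6.3** (randomisation and blinding): "The intervention allocation will be withheld from all study investigators and raters until after the conclusion of all measurements". The exceptions are narrow: "Other investigators will be blinded except due to adverse event or inadvertent event".
- **Section 6.1.1**: "randomization scheme will be kept only by biostatistician and intervention status will be known otherwise only by nutrition staff". The same section calls the PI a non-rater.
- **Section 8.2.4.2** (management of results): participants receive "a discharge summary and a debriefing on the day of discharge or as otherwise determined with the participant". The debriefing is to "give opportunity for researcher (PI / Metabolic Unit staff) to present clinical synopsis", to share parts of the participant's research data if the participant is interested, and to "provide education on diet given, general dietary recommendations, and summary of the intervention". The discharge summary it reviews includes UPDRS, MOCA and NMSS. Ketosis values, EEG and the cognitive, physiology and autonomic research measures are left out of the results given.

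Section 8.3 repeats the discharge-day timing, again allowing another arrangement. The final visit, with TUG, UPDRS, NMSS, cognitive tests, EEG and the exit survey, is two weeks after discharge (Sections 1.3 and 6.1.1).

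**The concern.** A planned, routine step appears to need knowledge that the blinding section forbids at that time. To teach a participant about the diet he or she was given, the person teaching must know which diet it was. The protocol names the PI as one of the people who may do this, on a default date that falls before the last set of measurements.

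At stake is the credibility of the week-3 data wherever they are compared by randomised diet. There are two routes. A blinded investigator learns the arm directly. Or the participant learns it, and then mentions it to the week-3 rater or is influenced by it when rating symptoms or performing effort-dependent tests.

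**Working it through.** No figure in the plan depends on this point, so the check is a comparison of the texts.

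**1. Who is covered, and until when.** Section 6.3 covers investigators and raters, and the restriction runs "until after the conclusion of all measurements, who will remain blinded to participant allocation for the duration of the study". Week 3 is a measurement visit, so the restriction is still in force at discharge. A planned debriefing is neither an adverse event nor an inadvertent event, so neither exception applies.

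**2. Who debriefs.** Section 8.2.4.2 offers two possibilities, the PI or Metabolic Unit staff.
- If the PI gives the diet education, an investigator outside the two groups named in Section 6.1.1 knows the arm before week 3. That conflicts with Sections 6.3 and 6.1.1.
- If an unblinded dietician gives it, no investigator need learn the arm, and the conflict does not arise by this route.

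**3. Whether the diet is disclosed.** Section 8.2.4.2 lists general dietary recommendations as a separate item, so the education on the diet given most naturally concerns the diet that participant received. This is an inference; the section does not state that allocation is revealed.

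**4. Whether the PI's knowledge could reach a rating.** Section 6.1.1 calls the PI a non-rater, but Section 8.3 has the PI administer UPDRS Parts 1, 2 and 4 and NMSS at screening. Section 1.3 lists total UPDRS and NMSS again at week 3, and nothing excludes the PI from administering them then.

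**5. Whether a participant's knowledge could reach a rating.** Section 6.3 tells participants to make no mention of their diet. It also provides that, if a rater is unblinded, the participant stays in the study but is discounted from the power calculation and marked separately for analysis. A routine debriefing raises the chance of triggering that rule. Section 6.3 also reports that participants in a similar blinded-diet study usually believed they were on the ketogenic diet. If that holds here, disclosure would tell many control participants something new.

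**6. Whether arm still matters at week 3.** It does. Section 9.4.2 plans a repeated measures ANCOVA of TUG over day 1, day 7 and week 3 with diet (ketogenic versus standard) as the between-subject effect.

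**7. Whether the powered comparison is touched.** Section 9.2 powers the day-7 TUG comparison with a difference of 4.5 s, SD 4 s (effect size 4.5/4 = 1.125) and two-sided alpha 0.0492. Exact t-test power is 0.784 at 13 per group and 0.815 at 14 per group, so the stated 28 reproduces. With 10% dropout, 28/0.90 = 31.1, which gives 32 in two equal groups. None of this changes. TUG is a morning test, so a debriefing held later that day or afterwards cannot affect it. The protocol does not state that order, however.

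**The case against.** The strongest reply is that week 3 is open by design. Section 4.2 justifies double-blinding for the inpatient part only, and after discharge everyone knowingly follows a ketogenic diet. Section 6.3 names investigators and raters, not participants. All of this stands. A reader might infer that telling participants their diet at discharge breaks the blinding promise; the documents do not support that. What is open after discharge is the home diet, though, and the inpatient allocation remains a factor in Section 9.4.2.

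Further points stand in part:

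- **Timing is flexible.** Sections 8.2.4.2 and 8.3 both allow another date, so a debriefing at week 3 already fits the text. Discharge day is nevertheless the default.
- **The debriefer may already be unblinded.** Section 6.1.2.1 counts the study dietician among Metabolic Unit staff. The conflict arises only if a blinded person gives the diet education, but the text names the PI and does not rule this out.
- **Counselling is mostly generic.** Section 8.3 describes advice on healthy eating and mentions no disclosure of arm. It does not withdraw the diet education in Section 8.2.4.2.
- **Much of the research data is withheld.** Ketosis, EEG and the cognitive, physiology and autonomic measures are excluded. UPDRS and NMSS are not. Section 8.3 repeats both on the day of discharge, although Section 1.3 lists total UPDRS and NMSS only at screening and week 3.
- **Raters have some protection.** Participants are told not to discuss their diet, and UPDRS-III has planned video rating by an outside specialist in scrambled day order (Section 4.1). This covers neither muscle tone nor the other week-3 tests.

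A second tempting inference is that the primary composite is compromised, because acceptability includes "effectiveness in symptom reduction, from all study participants at 3 weeks". That is speculative. The exit survey rates an openly ketogenic diet in all participants and is analysed descriptively, not by arm; hiding the inpatient diet would not make it blinded.

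**Conclusion.** The point holds as a conflict over investigator blinding, with a secondary risk to the week-3 comparison by arm. Followed in its default form and given by the PI or another blinded investigator, the debriefing in Section 8.2.4.2 cannot be squared with Sections 6.3 and 6.1.1. Through participants, it also gives the week-3 rater a route to the allocation.

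The conclusion rests on two readings: that education on the diet given refers to the diet that participant received, and that the debriefing takes place on its default date. If an unblinded dietician gives it, or if it is held after the week-3 ratings, the conflict disappears.

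The consequence is confined to week-3 effort-dependent, self-rated and rater-scored outcomes where the randomised diets are compared. Its size cannot be derived from the documents, and they do not show that every week-3 outcome in all 32 participants is affected. The day-7 TUG comparison and its sample size are untouched if testing precedes the debriefing. This is a low-severity point, worth making because the remedy is cheap.

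**What to change.** Amend Sections 8.2.4.2 and 8.3 so that they agree with Sections 6.1.1 and 6.3:

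1. Disclose the inpatient allocation and research rating scores only after the week-3 ratings and exit survey are complete.
2. At discharge, give only clinically needed results and the same home-diet instructions to both arms.
3. Have any diet-specific education at discharge given by the already unblinded nutrition staff, without revealing the arm.
4. State that day-7 testing is finished before any debriefing.

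The week-3 visit already exists, so this needs only a change of wording. The cost is that participants wait about two weeks for part of the debriefing.
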